7.1. IMP Discontinuation

7.1.1. Permanent Discontinuation

Permanent discontinuation of IMP occurs when the participant stops receiving IMP before the end of the study, and does not resume receiving IMP. The participant also must not have withdrawn informed consent.

The investigator will document the primary reason for early discontinuation of IMP.

Participants who permanently discontinue IMP will be encouraged to remain in the study and attend mandatory on-site visits as specified in the SoA (Table 1). If the participant cannot attend these visits for any reason, the study site will perform an early study discontinuation (ESD) visit and safety follow-up visits as specified in the SoA (Table 1).

Unless consent from the study has been withdrawn, the participant will attend an early treatment discontinuation (ETD) visit. Study sites will attempt to perform the ETD visit within 7 days after the participant's final IMP administration. After the ETD, the participant will continue participation in the study through the rest of the 36-week treatment period and may receive rescue therapy (defined in Section 6.8.3). At week 36, the participant will complete the EoTP visit assessments (Table 1). If the participant meets rollover eligibility requirements (described in the ARGX-113-2010 protocol) at the end of the EoTP visit, they will be invited to immediately enroll in the OLE study ARGX-113-2010. If the participant does not meet rollover eligibility requirements or chooses not to enroll in the OLE study, they will participate in the 7-week treatment-free follow-up period. Refer to the SoA (Table 1) for data to be collected at the time of discontinuation of IMP and follow-up and for any other evaluations that need to be completed.

The following circumstances will result in the permanent discontinuation of IMP:

- Participant becomes pregnant or intends to become pregnant (refer to Section 8.4.6).
- Investigator decides that discontinuing IMP is in the participant's best interest (the sponsor will be informed).
- Participant develops an SAE or AE that contraindicates further administration of IMP in the investigator's opinion.
- Unblinding occurred.
- Participant exhibits any of the conditions outlined in Section 6.8.3. In these cases, participant may start rescue therapy.
- Any of the liver chemistry criteria resulting in temporary IMP discontinuation outlined in Section 7.1.2 is met, and the event is considered by the investigator to be related to the IMP.

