IMP	Pharmaceutical form of an active ingredient or placebo, being tested or used as a reference in a clinical study.
Partial remission (PR)	The presence of only new transient lesions.
Relapse	Appearance of 3 or more new lesions a month (blisters, eczematous lesions, or urticarial plaques),

SGS	Statistical Analysis Plan	
ARGX-113-2009	Final and Interim Analysis	Final 4.0 of 04NOV2024

or at least 1 large (>10 cm diameter) eczematous lesion or urticarial plaque that does not heal within 1 week, or extension of established lesions or daily pruritus in a participant who has achieved CDA

Transient lesions New lesions that heal within 1 week or pruritus lasting less

than 1 week.

Treatment failure The absence of CDA after being administered oral prednisone at 0.75 mg/kg/day (or equivalent OCS)

for 3 weeks. The investigator has the option to add a fourth week of therapy with oral prednisone 0.75 or 1 mg/kg/day (or equivalent) (based on clinical judgment) before

declaring treatment failure

Treatment-emergent abnormality

Any post-baseline abnormality that was not present at baseline (e.g., hemoglobin normal at baseline and grade 1 post-baseline; glucose low at baseline and high post-baseline; QTcF]450; 480] ms at baseline and >500 ms post-baseline).

ARGX-113-2009 Final and Interim Analysis

Final 4.0 of 04NOV2024

TABLE OF CONTENTS

0	1 0		
Pro	tocol histor	у	3
List	of abbrevi	ations	4
		erms	
Tab		nts	
1.		on	
1.1	Study	objectives	15
	1.1.1	Part A	15
	1.1.2	Part B	16
1.2	Study	design	17
1.3	Expect	red sample size	17
1.4	Interin	analysis	18
	1.4.1	Futility analysis	18
	1.4.1.1	Endpoint used for the futility analysis	18
	1.4.1.2	Missing data imputation	18
	1.4.1.3	Statistical analysis	19
	1.4.1.4	Futility analysis recommendation algorithm	19
	1.4.2	Sample size re-adjustment	20
	1.4.2.1	Statistical calculation	20
	1.4.2.2	Sample size re-assessment algorithm	21
	1.4.3	Control of the type I error for key secondary endpoints	21
	1.4.3.1	Statistical analysis	21
	1.4.3.2 secondary	Algorithm to adapt the methodology to control type I error for key rendpoints	22
	1.4.4	Data access plan	22
	1.4.4.1	Personnel who will perform the interim analyses	22
	1.4.4.2	Personnel who will have access to interim results	22
	1.4.4.3	Access control	22
	1.4.4.4	Information to be disseminated outside the AC	23
	1.4.4.5	Recipient of the recommendation	23
1.5	Softwa	re	23
1.6	Valida	tion model	23
2.	General n	nethodology	24

ARGX-113-2009

Final and Interim Analysis

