2.2.5 Worst-case

[figure not shown]
A worst-case analysis visit will be created for parameters for which abnormalities and/or toxicity grades are defined to summarize values considered as the worst-case. For abnormalities it is derived per parameter and in case both the lowest and the highest values are considered abnormal, a participant can have 2 worst-case analysis visits for a same parameter. For toxicity grades the worst-case is the value associated to the highest toxicity grade and is derived per parameter and toxicity direction (hypo/hyper).

All non-missing post-baseline values, including unscheduled assessments and FU visits will be considered when deriving the worst-case analysis visit.

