4.3.3 Presentation of results

All pharmacodynamic endpoints will be summarized by means of descriptive statistics at each analysis visit. Actual values, changes from baseline and percent changes from baseline will be tabulated.

Tables with descriptive statistics will be presented including all available data and will be repeated for a subset of data in which samples are excluded if taken later than 2 weeks (14 days) after the previous IMP administration.

SGS	Statistical Analysis Plan	
ARGX-113-2009	Final and Interim Analysis	Final 4.0 of 04NOV2024

Also, the same subgroup analyses will be performed as for efficacy. For the final analysis of Part A data, only the following subgroups are of interest:

[figure not shown]
- Disease history (newly diagnosed versus relapsing)
- Disease severity as per IGA-BP at screening (moderate versus severe)
- BPDAI activity score at baseline: <20, 20-56, >56
- Age at informed consent (18 <65, 65 <75, 75 <85, >=85)

Listings will be created for total IgG, and anti-BP antibodies results over time. Listings will always show the non-imputed results.

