5.1.2 Derivation rules

Treatment-emergent adverse events (TEAE) are defined as AEs starting within 60 days of an administration of IMP. Post-TEAEs are AEs starting after first administration of IMP that are not TEAEs.

Based on their start date/time, AEs will be allocated to the phase during which they started. Each AE will therefore be reported in only one phase. In case the AE start date/time is incomplete or missing and the AE could consequently be allocated to more than one phase, a worst-case allocation will be done as detailed below:

 Treatment phase vs. non-treatment phase: the AE will be allocated to the treatment phase unless the available parts of the AE start or stop date/time provide evidence for allocating to the non-treatment phase.

A death case is defined as an AE with outcome 'fatal'.

An AE for which the IMP was discontinued is defined as an AE with action taken 'drug withdrawn'.

AEs with missing treatment, prednisone or procedure relatedness will be considered as treatment-related, prednisone-related, or procedure-related respectively.

[figure not shown]
AEs with missing seriousness will be considered as serious AEs.

Adverse events of special interest will be defined using MedDRA system organ class 'Infections and infestations'.

Injection-related reactions (IRRs) will be defined as all AEs with MedDRA preferred terms that are listed in either:

- Hypersensitivity standardized MedDRA query (SMQ) (broad selection)
- Anaphylactic reaction (SMQ) (broad selection)
- Extravasation events (injections, infusions and implants) (SMQ) (broad selection), excluding implants

AND occurring within 48 hours of an administration, or within 2 days in case no AE start time is available. In case of (partially) missing AE start date, the AE will be considered as an IRR, unless the available parts of the AE start date provide evidence it did not occur within 48 hours of an injection.

Injection site reactions (ISR) will be defined as all AEs with a MedDRA high level term of "Injection site reaction", regardless of the time of AE onset relative to an administration.

AE onset and duration will be calculated as follows when start and stop dates are fully known:

- AE onset day (vs. first administration) =
 - AE start date ≥ date of first administration: AE start date date of first IMP administration + 1 day
 - AE start date < date of first administration: AE start date date of first IMP administration
- AE duration (days) =

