5.2.3 Presentation of results

The statistical analysis will present results in standardized units, except for eGFR that will be presented in mL/min/1.73m².

Continuous laboratory parameters will be summarized by means of descriptive statistics at each analysis visit. Actual values and changes from baseline will be shown in the same table. For albumin and low-density lipoprotein-cholesterol (LDL-C) also percent changes vs baseline will be shown.

Laboratory abnormalities for biochemistry and hematology parameters will be presented as a cross-tabulation (shift table) of the abnormality at each post-baseline analysis visit and at the worst-case analysis visit versus the baseline abnormality. This table will also show numbers of participants with treatment-emergent abnormalities (see Definition of terms). The denominator for the percentage is the total number of participants per treatment and per analysis visit in the safety analysis set. Tables for laboratory abnormalities will be restricted to biochemistry and hematology parameters.

Laboratory toxicity grades will be presented as a cross-tabulation (shift table) of the toxicity (NCI-CTCAE grades) at each post-baseline analysis visit and at the worst-case analysis visit versus the baseline toxicity. This table will also show numbers and cumulative numbers over decreasing toxicity grading of participants with treatment-emergent toxicities. The denominator for the percentage is the total number of

participants per treatment and per analysis visit in the safety analysis set. Parameters having toxicity grades defined in both directions (hypo and hyper) will be shown by direction.

All laboratory data will be listed, but only for participants with any post-baseline abnormality or toxicity or any overall interpretation of blood sample determined as clinically significant by the investigator, based on the sample for biochemistry or hematology parameters.

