5.4.2 Derivation rules

When the ECG assessment date/time is registered down to the level of seconds, the part in seconds will not be considered for analysis purposes (e.g. selection of baseline assessment, allocation to phases/periods).

Abnormalities for HR, QRS and PR interval are defined in below table.

	HR (bpm)	PR (ms)	QRS (ms)
Low	<40	<120	((₹)
Normal	40-100	120-220	0-120
High	>100	>220	>120

Note: For the worst-case analysis visit, as defined in section 2.2.5, an additional category low + high is defined in case there are both low and high post-baseline values.

For QTcF and QTcB interval (ms), the following categories are defined:

- Actual values:
 - $\circ \leq 450 \text{ (normal)}$
 - 0]450; 480]
 - 0 [480; 500]
 - 0 > 500
- Changes:
 - $\circ \leq 30 \text{ (normal)}$
 - 0 [30; 60]
 - 0 > 60

Note: The worst-case, as defined in section 2.2.5, is the highest post-baseline value and associated change.

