5.4.3 Presentation of results

Uncorrected QT interval and RR interval will only be listed.

Continuous ECG parameters will be summarized by means of descriptive statistics at each analysis visit. Actual values and changes from baseline will be shown in the same table.

Abnormalities of the actual values will be presented as a cross-tabulation of the abnormality at each post-baseline analysis visit, and at the worst-case analysis visit

SGS	Statistical Analysis Plan	
ARGX-113-2009	Final and Interim Analysis	Final 4.0 of 04NOV2024

versus the baseline abnormality. This table will also show numbers and cumulative numbers over decreasing abnormalities (QTcF and QTcB only) of participants with treatment-emergent abnormalities. The denominator for the percentage is the total number of participants per treatment and per analysis visit in the safety analysis set.

Abnormalities of the QTcF and QTcB changes from baseline will be presented as a tabulation of the change from baseline abnormality at each post-baseline analysis visit and at the worst-case analysis visit. This table will also show cumulative numbers over decreasing change from baseline abnormalities of participants. The denominator for the percentage is the total number of participants per treatment and per analysis visit in the safety analysis set.

All ECG data will be listed, but only for participants with any post-baseline abnormality or any overall interpretation determined as clinically significant by the investigator.

SGS	Statistical Analysis Plan	
ARGX-113-2009	Final and Interim Analysis	Final 4.0 of 04NOV2024

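### Treatment-emergent laboratory, vital-sign and ECG abnormalities have no end date, while treatment-emergent adverse events end 60 days after IMP, so the worst-case counts mix on-drug values with values long after IMP or on rescue.

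*SAP*

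**What the plan says.** The SAP Definition of terms describes a treatment-emergent abnormality as "Any post-baseline abnormality that was not present at baseline". Its examples include haemoglobin, glucose and QTcF, so it covers laboratory and ECG data. SAP 5.2.3 and 5.3.3 cite this definition for the laboratory and vital-sign shift tables, in the same words: "This table will also show numbers of participants with treatment-emergent abnormalities (see Definition of terms"). SAP 5.2.3 also counts treatment-emergent toxicity grades, and 5.4.3 counts treatment-emergent ECG abnormalities. None of these sections sets a limit in time since IMP or at the start of rescue.

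On the worst-case row, SAP 2.2.5 states: "All non-missing post-baseline values, including unscheduled assessments and FU visits will be considered when deriving the worst-case analysis visit". For QTc, SAP 5.4.2 adds: "The worst-case, as defined in section 2.2.5, is the highest post-baseline value and associated change".

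For adverse events, SAP 5.1.2 is different: "Treatment-emergent adverse events (TEAE) are defined as AEs starting within 60 days of an administration of IMP". SAP 5.1.3 tabulates later events as post-TEAEs and again among all AEs of the treatment and follow-up phases.

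Protocol 7.1.1 keeps early stoppers under observation: "After the ETD, the participant will continue participation in the study through the rest of the 36-week treatment period and may receive rescue therapy". Protocol 6.8.3 lists conventional immunosuppressants and dapsone among the rescue options. The Schedule of Activities has early stoppers attend the mandatory on-site visits, where chemistry, haematology and vital signs are taken.

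**The concern.** One label carries two windows within the same set of safety outputs. Protocol 8.3.6.1 requires clinically significant laboratory changes to be recorded as AEs. If such a change arises 100 days after the last dose, on rescue, the AE is a post-TEAE while the laboratory value behind it is a treatment-emergent abnormality.

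What is at stake is the comparison between arms in the worst-case row. Rescue follows treatment failure, a second relapse or steroid toxicity, so its frequency may differ by arm. The plan itself compares the proportion rescued before week 36 as a secondary efficacy endpoint. A worst-case count that pools on-drug and on-rescue values does not describe either arm's experience of the drug alone.

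The SAP separates such data elsewhere. Table 1 defines on-IMP and off-IMP periods. The pharmacodynamic tables are "repeated for a subset of data in which samples are excluded if taken later than 2 weeks (14 days) after the previous IMP administration". The glucocorticoid toxicity index, which Protocol 8.3.9 classes as an additional safety assessment, uses only assessments up to the start of rescue (SAP 4.1.4, item 17). The pharmacodynamic rule serves a different purpose and uses a different window, so it shows only that such a split is feasible.

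**Working it through.** The plan states no figure on this point to reproduce. The check compares two windows by day arithmetic.

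**Inputs**
- Chemistry and haematology after baseline (Protocol Table 1): days 8, 15, 29, 57, 85, 113, 141, 169, 183, 197, 225 and 253, which is 12 visits to week 36.
- Follow-up visits, for those who do not roll over: week 39 = 39 × 7 + 1 = day 274 and week 43 = 43 × 7 + 1 = day 302, which makes 14.
- Scheduled post-baseline ECGs: days 183 and 253 (SAP Table 2 footnote). None is scheduled in follow-up.
- Vital signs follow the laboratory days plus day 22, which changes none of the late counts below.
- The last IMP day is assumed and shown as a range. Protocol 6.8.1.3 places treatment failure at about 1 + 3 = 4 to 3 + 3 + 1 = 7 weeks, so days 29 to 50 represent the earliest failures.

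**Formulas**
- TEAE window closes on day (last IMP day + 60).
- Excess = 253 (or 302) minus that day.
- Late visits are scheduled days after it.

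| Last IMP week (day) | Window closes | Excess days to week 36 / week 43 | Late lab visits of 12 / of 14 | Late ECGs of 2 |
|---|---|---|---|---|
| 4 (29) | 89 | 164 / 213 | 7 / 9 | 2 |
| 7 (50) | 110 | 143 / 192 | 7 / 9 | 2 |
| 12 (85) | 145 | 108 / 157 | 5 / 7 | 2 |
| 20 (141) | 201 | 52 / 101 | 2 / 4 | 1 |
| 24 (169) | 229 | 24 / 73 | 1 / 3 | 1 |
| 27 (190) | 250 | 3 / 52 | 1 / 3 | 1 |
| 28 (197) | 257 | 0 / 45 | 0 / 2 | 0 |
| 34 (239) | 299 | 0 / 3 | 0 / 1 | 0 |
| 35 (246), completer | 306 | 0 / 0 | 0 / 0 | 0 |

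For a completer, week 43 is 302 − 246 = 56 days after the last dose. Using the visit windows at their extremes it is (302 + 3) − (246 − 2) = 61 days, one day outside.

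**Rescue inside the window.** The early treatment discontinuation visit is targeted within 7 days of the last dose, and rescue may start there. With rescue starting 0 to 7 days after the last dose, 60 − 7 = 53 to 60 − 0 = 60 days of it fall inside the TEAE window. A cut-off based on IMP alone therefore does not isolate rescue.

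**The case against.** The strongest case on the other side has five parts.

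- **Both rules are explicit.** Programming is unambiguous, and the abnormality rule spans the same time as the SAP's overall AE tables. This stands: the problem is a mismatch between outputs, not a contradiction.
- **Timing is visible elsewhere.** The shift tables show each analysis visit, clinically significant changes also pass through the AE split, and listings of laboratory results, IMP dosing and rescue allow individual attribution. This stands, but by-visit rows show study week, not time since IMP or rescue status, and they do not repair the worst-case treatment-emergent count.
- **The analyses are descriptive** (Protocol 9.3.3.3). This stands: no test or decision rule depends on these tables.
- **A 60-day cut-off would not remove rescue.** This also stands, as the 53 to 60 days above show.
- **A cut-off has a cost.** These tables report percentages of participants. If one arm has more early stoppers, a restricted window gives it fewer visits and fewer chances to record an abnormality. This stands, and it argues against replacing the all-post-baseline version.

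A reader might infer that AEs cease to be reported after 60 days. They do not: only the label changes. A reader might also infer a definite shift in favour of efgartigimod, or a hidden laboratory signal. The documents do not support that. They give neither rescue rates by arm nor abnormality rates on rescue, rescue may be corticosteroids alone, and early on-drug visits are shown by arm.

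**Conclusion.** The mismatch is real and confined to participants who stop IMP early: last dose up to about week 27 for laboratory, vital-sign and ECG data to week 36, and up to about week 34 for laboratory and vital-sign data if they are followed to week 43. For the earliest failures, more than half of the scheduled post-baseline laboratory visits, and both scheduled ECGs, lie beyond the TEAE window yet feed the treatment-emergent and worst-case counts. These figures rest on nominal visit days and assumed last-dose days. The number of participants affected, and any net effect on the comparison between arms, cannot be derived from the documents. That rescue differs by arm is plausible but not established. The change is worth making because it is cheap and loses no data. It does not affect the primary analysis or error control.

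**What to change.** In the SAP Definition of terms and sections 2.2.5, 5.2.3, 5.3.3 and 5.4.3:

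- Split treatment-emergent abnormalities, toxicity grades and the worst-case row into (a) first IMP to last IMP + 60 days and (b) later, labelled post-treatment-emergent, to match the AE tables.
- Flag values on or after the start of rescue therapy, since rescue can begin within window (a).
- Show the number of participants, or the follow-up time at risk, with window (a), because follow-up in it may be unequal between arms.
- Keep the all-post-baseline version alongside.

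The cost is SAP wording, two derived flags and a repeat of existing shift tables. The downsides are more output and the unequal follow-up in window (a). No data collection or clinical rule changes. The amendment is best made before Part B is unblinded.

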5.3 VITAL SIGNS

5.3.1 Available data

The following vital signs parameters are collected over time: supine systolic (SBP) and diastolic blood pressure (DBP), heart rate, body temperature, BMI and weight.

5.3.2 Derivation rules

Abnormalities are defined in below table.

	SBP (mmHg)	DBP (mmHg)	Temperature (°C)
Low	<90	<45	<35.8
Normal	90-150	45-90	35.8-37.5
High	>150	>90	>37.5

Note: For the worst-case analysis visits, as defined in section 2.2.5, an additional category low + high is defined in case there are both low and high post-baseline values.

BMI (kg/m^2) will be derived as = $(body weight (kg)) / (height at screening (m))^2$. Post-baseline values will only be used in the C-GTI derivations.

5.3.3 Presentation of results

Vital signs parameters (without BMI) will be summarized by means of descriptive statistics at each analysis visit. Actual values and changes from baseline will be shown in the same table.

Abnormalities will be presented as a cross-tabulation of the abnormality at each post-baseline analysis visit and at the worst-case analysis visit versus the baseline abnormality. This table will also show numbers of participants with treatment-emergent abnormalities (see Definition of terms).

All vital signs data (without BMI) will be listed, but only for participants with any post-baseline abnormality or any reading determined as clinically significant by the investigator.

SGS	Statistical Analysis Plan	
ARGX-113-2009	Final and Interim Analysis	Final 4.0 of 04NOV2024

5.4 ELECTROCARDIOGRAMS

5.4.1 Available data

At a minimum, the following electrocardiogram (ECG) parameters will be collected over time: QRS interval, PR interval, RR interval, QT interval, QTcF, QTcB, ventricular rate (HR), and overall interpretation (by investigator and by ECG vendor).

